7.3 Follow-up

7.3.1. Period 2 (Study Assessment Day 4 through Study Assessment Day 10)

Documentation of receipt of PRBC transfusion(s) will be provided on an eCRF. If the study subject has NOT received ≥ 10 PRBC transfusions (see Section 9.3.1), proceed with required assessments.

Required assessments [following confirmation that subject is still receiving ganciclovir (e.g., that the ganciclovir has not been permanently discontinued)]: 1) virology blood

specimens for CMV viral load (required amount of whole blood for CMV PCR is 0.5 mL); 2) CMV detection from noninvasive urine specimen (if obtainable); 3) ganciclovir dosing information (mg/dose, dosing interval, subject weight).

Optional assessments (if being drawn for clinical reasons; any laboratory value obtained during the window will suffice, with an effort being made to capture the most abnormal value): 1) hematology labs (WBC with differential, hemoglobin, platelet count); 2) chemistry labs (AST, ALT); 3) serum creatinine.

Study Assessments (as described)	Optional Assessments*
Virology blood specimens for CMV viral load	Hematology labs (WBC with differential, hemoglobin, platelet count)
If obtainable, CMV detection from noninvasive urine specimen (e.g., bagged, from indwelling foley catheter, excess clinical specimen, etc.)	Chemistry labs (AST, ALT)
Ganciclovir dosing information (mg/dose, dosing interval, subject weight)	Serum creatinine

* If being drawn for clinical reasons; any laboratory value obtained during the window will suffice, with an effort being made to capture the most abnormal value

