Both whole blood for CMV PCR and urine for CMV assessment will be obtained serially through Study Assessment Period 7 as long as the subject is receiving intravenous ganciclovir therapy (that is, until the ganciclovir is permanently discontinued). These specimens will be used to determine viral load and, as indicated, ganciclovir resistance. At each sample collection time, urine will be split into two aliquots. These aliquots will be available for CMV detection as appropriate, based upon whole blood viral loads. Specimens will then be available for subsequent testing for ganciclovir resistance in the UAB Virology Resistance Laboratory. Since ganciclovir is a renally excreted drug, serum creatinine will be drawn for the research protocol on the day that the ganciclovir pharmacokinetic specimens are obtained in order to calculate creatinine clearance using a method such as the modified Schwartz formula, and thus correlate ganciclovir clearance with renal function. Otherwise, data from hematology assessments (WBC count and differential, hemoglobin, platelet count) and from chemistry labs (serum creatinine, ALT, and AST) will be recorded on the study case report forms each study assessment period if they are being obtained for clinical reasons, but will not be drawn only for the purposes of the study. Ganciclovir dosing information (mg/dose, dosing interval, and subject weight) will be recorded on the day of the pharmacokinetic blood draws. Once a subject is successfully enrolled into the study the ganciclovir dosing information (mg/dose and dosing interval) will be recorded from the start of clinical treatment of ganciclovir until date of enrollment. After enrollment ganciclovir dosing information (mg/dose and dosing interval) will be captured from Study Assessment Period 1 through the Study Assessment Period 7; as long as the subject is receiving intravenous ganciclovir therapy.

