8.2.1.1. CMV Viral Load/Resistance Testing

[figure not shown]
Assessment of CMV viral load in whole blood will be conducted at the UAB Central Laboratory. The required amount of whole blood for CMV PCR is 0.5 mL. Whole blood will be collected at each study visit from Period 1 through Period 5. Whole blood will also be collected at the Period 6 study visit if the

subject weighs at least 600 grams, and at the Period 7 study visit if the subject weighs at least 650 grams.

Urine collection by noninvasive mechanism (e.g., bagged, indwelling foley catheter, excess clinical specimen, etc.) will be attempted at each study visit. If urine is obtainable, it will be frozen and sent to the UAB Central Laboratory for processing. If an attempt to obtain urine for CMV detection is unsuccessful, study staff will document the failed attempt on a source document. All specimens collected will be sent to the UAB Central Laboratory.

Viral detection assays will be performed in the UAB Central Laboratory. These assays and tests are in clinical and research use already in the Central Laboratory. The detection of CMV DNA will be performed using the CMV two primer Taqman assay already employed regularly in our laboratory. The detection limit of our real-time PCR assay, as determined by the sensitivity titration analysis, is 10 genomic equivalents per reaction. The results of 10 different runs on different days are shown in the Table below. Regression analysis shows a very high correlation coefficient (0.9996) for the 6 log concentration range (see Figure below).

genome equivalents	log(10)	# +/10	ct(mean)	std
1000000	6	10/10	18.362	0.085609
100000	5	10/10	21.476	0.155863
10000	4	10/10	24.855	0.187157
1000	3	10/10	28.321	0.305449
100	2	10/10	31.869	0.2283
10	1	10/10	35.283	0.606045

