9.3 Halting Rules

9.3.1 Discontinue of Study participation for individual subject.

Subjects who experience significant problems with blood draws may be withdrawn from any future sampling. Transfusions are expected in hospitalized premature infants. One study reported that extremely premature neonates receive an average of 5.2 ± 4.2 transfusions over a six week period.³¹ Other trials have reported similar numbers of transfusions in this population.^{32,33} It is possible that even higher numbers of transfusions might be experienced in

the at-risk population in this sampling study since they are receiving the myelosuppressive drug ganciclovir as part of clinical care. Transfusions are not associated with long-term sequelae.³³ Nevertheless, if a study subject receives ≥ 10 PRBC transfusions during the course of the study, all future study-related blood draws will not be performed.

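### The 10-transfusion gate in Protocol Section 7 covers all required assessments, but the rule it cites (9.3.1) stops only study blood draws, so late urine and dosing records may be kept at some sites and dropped at others

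*Protocol*

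**What the plan says.** The same sentence appears in Protocol Sections 7.3.1 to 7.3.5 and 7.4.1: "If the study subject has NOT received ≥ 10 PRBC transfusions (see Section 9.3.1), proceed with required assessments". In Periods 2, 3, 5, 6 and 7 the required list has three items. The first is blood for CMV viral load. The other two take no blood: "2) CMV detection from noninvasive urine specimen (if obtainable); 3) ganciclovir dosing information (mg/dose, dosing interval, subject weight"). Clinical hematology and chemistry values are listed separately as optional. In Period 4 the gate stands above a single bullet list that does not separate required from optional items.

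Section 9.3.1 says that "if a study subject receives ≥ 10 PRBC transfusions during the course of the study, all future study-related blood draws will not be performed". It does not mention urine or dosing records.

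Other sections set no transfusion condition:

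- Section 4, specimens: "Both whole blood for CMV PCR and urine for CMV assessment will be obtained serially through Study Assessment Period 7", while the infant is on intravenous ganciclovir.
- Section 4, dosing information: it "will be captured from Study Assessment Period 1 through the Study Assessment Period 7; as long as the subject is receiving intravenous ganciclovir therapy".
- Section 8.2.1.1: "Urine collection by noninvasive mechanism (e.g., bagged, indwelling foley catheter, excess clinical specimen, etc.) will be attempted at each study visit".
- Appendix A footnote a, repeated under SAP Table 1: the only condition for Periods 2 to 7 is that the infant still receives ganciclovir.

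**The concern.** The gate names 9.3.1 as its source but reaches further. Read literally, a site would stop urine collection and dose and weight recording once an infant has had 10 transfusions. Neither item draws blood, and the documents give no reason to stop either. A site working from 9.3.1, Section 4, Section 8.2.1.1 or the schedule of events would continue both.

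Two things are at stake. Clearance of CMV in urine is a secondary endpoint. Dose and duration of therapy enter the exploratory resistance objective. Sections 2.3.1, 9.3.1 and 9.3.2 link transfusion counts to underlying illness and to a myelosuppressive drug, so gaps that begin at the tenth transfusion could be related to severity. The planned GEE analysis is, in its standard form, not protected against missingness of that kind.

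There is also a practical side. SAP Appendix C, item 4.2.2, has the eCRFs compared with both the schedule of events and the protocol narrative, and on this point those two disagree.

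**Working it through.** **Step 1: the texts side by side, for an infant with 10 or more transfusions who is still on ganciclovir**

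| Item | Section 7, read literally | Section 9.3.1 | Section 4, 8.2.1.1, Appendix A, SAP Table 1 |
|---|---|---|---|
| Study blood for viral load | stops | stops | no transfusion condition |
| Non-invasive urine | stops | not mentioned | no transfusion condition |
| Dose, interval, weight | stops | not mentioned | no transfusion condition |
| PRBC record | kept (precedes the gate) | not mentioned | no transfusion condition |
| Optional clinical labs | outside the gate, except Period 4 (ambiguous) | not mentioned | no transfusion condition |

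Section 7 and 9.3.1 agree on study blood. They part on urine and dosing records.

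**Step 2: the protocol's own transfusion figure**

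Section 9.3.2 uses a Poisson count with mean 5. P(X > 5) = 0.3840, against 0.384 stated, so it reproduces. The point contests no figure in the plan; the transfusion data serve only to size the group.

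**Step 3: how many infants might reach 10**

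Inputs: mean 5.2 and SD 4.2 over six weeks (Section 9.3.1); 32 infants (Section 4). Assumptions: a constant rate, so that the mean by day d is 5.2 × d/42, and either a Poisson count or a negative binomial matched to the quoted SD.

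The quoted SD gives a variance of 4.2² = 17.64, against 5.2 under Poisson, so the cited data are overdispersed and the negative binomial fits them better. Its size parameter is k = 5.2² / (17.64 − 5.2) = 27.04 / 12.44 = 2.17, held fixed over time.

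| By day | Mean | P(≥10), Poisson | P(≥10), negative binomial | Expected of 32 |
|---|---|---|---|---|
| 14 | 1.73 | <0.0001 | 0.0025 | <0.1 |
| 28 | 3.47 | 0.0031 | 0.0457 | 0.1 to 1.5 |
| 42 | 5.20 | 0.0397 | 0.1420 | 1.3 to 4.5 |

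For Day 42: 32 × 0.0397 = 1.3 and 32 × 0.1420 = 4.5. For Day 28: 32 × 0.0031 = 0.1 and 32 × 0.0457 = 1.5.

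As a sensitivity check, the halting table's alternative of a Poisson mean of 7 over the full course gives P(≥10) = 0.1695, or 5.4 of 32.

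**Step 4: from reaching 10 to losing data**

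The Day 42 row applies only if every infant is still on study and on ganciclovir at that point. Section 2.1 describes two to four weeks of therapy as usual, and collection after Period 1 is required only while ganciclovir continues. An infant who crosses the threshold during Days 39 to 42 with Period 7 already done loses nothing. The counts are therefore upper limits on the infants affected under each model.

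**The case against.** The best defence is that Section 7 says when to proceed and never says what to omit. It sends the reader to 9.3.1, which names blood draws only, so a careful site would keep collecting urine and dosing records. That stands: data loss follows from one reading, and what the documents establish is a risk of inconsistent practice.

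Conversely, a wider stop may have been meant. Section 9.3.1 is headed as discontinuing an individual's study participation. The silence of Section 4, Section 8.2.1.1 and Appendix A is also not decisive, because they omit the transfusion condition for blood as well. The intended scope is therefore for the sponsor to confirm.

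A reader might infer more than the documents support:

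- **That heavily transfused infants drop out of the urine endpoint.** They do not. Urine obtained before the tenth transfusion stays, and GEE uses the repeated observations available. Section 4 also makes urine testing depend on whole-blood viral loads, so urine collected after study blood has stopped may add less.
- **That the primary analysis is damaged.** The required PK profile falls within Study Assessment Days 1 to 5, when 10 transfusions is very unlikely.
- **That neutrophil data are lost.** Hematology is optional and outside the gate in five of the six periods. What could be missing is the late dose and weight history to set beside it.
- **That the infants affected are the most exposed to ganciclovir.** The protocol says that a myelosuppressive drug may raise transfusion numbers in this population. It does not say that an infant's count tracks that infant's exposure.

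Finally, the transfusion rate comes from extremely premature neonates, while two of the four strata are 28 weeks or more, so it may not carry over to the whole sample.

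**Conclusion.** The inconsistency is real and appears in all six follow-up subsections: the gate is wider than the rule it cites. The consequence is limited to possible, site-dependent and perhaps severity-related gaps in late urine specimens and late dose and weight records. AUC12, data from before the tenth transfusion, PRBC records and (Period 4 aside) optional clinical labs are not affected.

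With the usual two to four weeks of therapy, the expected number reaching the threshold runs from below 0.1 to about 1.5 infants. The range of 1.3 to 4.5 needs all 32 to remain on study and on ganciclovir to Day 42. Both rest on the cited transfusion rate, a constant rate over time, and the two count models. Severity is minor.

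**What to change.** Reword the gate in 7.3.1 to 7.3.5 and 7.4.1 to match 9.3.1, so that it covers study-related blood draws only. Leave the 10-transfusion stop on those draws as it is. Add that non-invasive urine and ganciclovir dose, interval and weight recording continue on the existing condition that the infant still receives ganciclovir. In 7.3.3 (Period 4), make clear which bullets the gate covers.

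Check that any eDES visit rule agrees. The SAP lists only a transfusion alert among its notifications, and the text available does not show whether a gating rule exists.

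If the sponsor did intend a wider stop, then 9.3.1, Section 4, Section 8.2.1.1, Appendix A and SAP Table 1 must be changed to agree.

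The cost is one sentence in six places, a clarification for Period 4 and an eDES check. It adds no blood, visits or procedures, and only a little urine and chart work for a few infants at most.

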7.3.2. Period 3 (Study Assessment Day 11 through Study Assessment Day 17)

Documentation of receipt of PRBC transfusion(s) will be provided on an eCRF. If the study subject has NOT received ≥ 10 PRBC transfusions (see Section 9.3.1), proceed with required assessments.

Required assessments [following confirmation that subject is still receiving ganciclovir (e.g., that the ganciclovir has not been permanently discontinued)]: 1) virology blood specimens for CMV viral load (required amount of whole blood for CMV PCR is 0.5 mL); 2) CMV detection from noninvasive urine specimen (if obtainable); 3) ganciclovir dosing information (mg/dose, dosing interval, subject weight).

Optional assessments (if being drawn for clinical reasons; any laboratory value obtained during the window will suffice, with an effort being made to capture the most abnormal

value): 1) hematology labs (WBC with differential, hemoglobin, platelet count); 2) chemistry labs (AST, ALT); 3) serum creatinine.

Study Assessments (as described)	Optional Assessments*
Virology blood specimens for CMV viral load	Hematology labs (WBC with differential, hemoglobin, platelet count)
If obtainable, CMV detection from noninvasive urine specimen (e.g., bagged, from indwelling foley catheter, excess clinical specimen, etc.)	Chemistry labs (AST, ALT)
Ganciclovir dosing information (mg/dose, dosing interval, subject weight)	Serum creatinine

* If being drawn for clinical reasons; any laboratory value obtained during the window will suffice, with an effort being made to capture the most abnormal value

7.3.3. Period 4 (Study Assessment Day 18 through Study Assessment Day 24)

- Documentation of receipt of PRBC transfusion(s) will be provided on an eCRF. If the study subject has NOT received ≥ 10 PRBC transfusions (see Section 9.3.1), proceed with required assessments.
- Confirmation that subject is still receiving ganciclovir (e.g., that the ganciclovir has not been permanently discontinued)
- Hematology labs (see Section 8.2)
 - WBC with differential, hemoglobin, and platelet count, if being drawn for clinical reasons; any laboratory value obtained during the window will suffice, with an effort being made to capture the most abnormal value
- Chemistry labs (see Section 8.2)
 - AST and ALT, if being drawn for clinical reasons; any laboratory value obtained during the window will suffice, with an effort being made to capture the most abnormal value
- Serum creatinine (see Section 8.2)
 - Obtain if the ganciclovir pharmacokinetics are being obtained during this study assessment period

- To be drawn on the calendar day that ganciclovir PKs are being drawn
- Ganciclovir pharmacokinetics, if desired by the treating physicians and the subject weighs \geq 575 grams at that time (see Section 8.2.2.2.)
 - Ganciclovir concentrations may be obtained around one dose in this assessment window (Study Assessment Day 18 through Study Assessment Day 24)
 - Timepoints for pharmacokinetic draws: 0h (immediately prior to IV ganciclovir dose; window: -15 min), 1h (immediately after the end of the IV ganciclovir dose; window: +15 min), 2-3h, 5-7h, and 10-12h
 - Required amount of whole blood for plasma ganciclovir determination at each timepoint is 200 μ L (0.2 mL)
 - If subject weighs $<$ 575 grams, the second set of PK draws cannot be performed
- Virology specimens (see Sections 8.2.2.1.)
 - Blood for CMV quantitative PCR will be obtained (required amount of whole blood for CMV PCR is 0.5 mL)
 - If obtainable, urine for CMV detection will be obtained non-invasively (e.g., bagged, from indwelling foley catheter, excess clinical specimen, etc.)
- Ganciclovir dosing information
 - mg/dose
 - Dosing interval
 - Subject weight

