8.2 Laboratory Evaluations

Chemistry labs (serum creatinine) will be drawn on the calendar day that ganciclovir PKs are being drawn; required amount of whole blood for serum creatinine is 0.25 mL. All other chemistry labs (serum creatinine, AST, and ALT) and hematology labs (WBC with differential, hemoglobin, platelet count) will be recorded on eCRFs if they have been drawn for clinical reasons; any laboratory value obtained during the window will suffice, with an effort being made to capture the most abnormal value.

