Ganciclovir pharmacokinetics		X ^h		X ^{i,j}			
Virology blood specimens for CMV viral load ^k	X ^l	X ^l	X ^l	X ^l	X ^l	X ^{l,m}	X ^{l,n}
CMV detection from noninvasive urine specimen	X ^o	X ^o	X ^o	X ^o	X ^o	X ^o	X ^o
Ganciclovir dosing information	X ^p	X ^p	X ^p	X ^p	X ^p	X ^p	X ^p
PRBC transfusion assessment	X ^q	X ^q	X ^q	X ^q	X ^q	X ^q	X ^q

Assessment for AEs or SAEs		X	X	X	X	X	X
Total volume of blood required for study procedures	1.75 mL	0.5 mL	0.5 mL	0.5 mL or 1.5 mL ⁱ	0.5 mL	0.5 mL	0.5 mL

a) Data and specimens in this column to be captured if subject still receiving ganciclovir as clinical treatment

b) Gestational age at delivery, date of birth, day of life at initiation of IV ganciclovir therapy, gender, race, ethnicity, birth weight, weight at enrollment, length in centimeters at enrollment, reason ganciclovir being administered, ganciclovir dose and dosing frequency, manufacturer of the ganciclovir lot utilized at the treating facility, date ganciclovir therapy was initiated

c) Window: Birth through Study Assessment Day 3)

d) WBC with differential, hemoglobin, platelet count. Optional laboratory draws are not required by the protocol, and so no documentation on a source document will be required.

e) If being drawn for clinical reasons; any laboratory value obtained during the window will suffice, with an effort being made to capture the most abnormal value. Optional laboratory draws are not required by the protocol, and so no documentation on a source document will be required.

f) AST, ALT. Optional laboratory draws are not required by the protocol, and so no documentation on a source document will be required.

g) To be drawn on the calendar day that ganciclovir PKs are being drawn. Study related laboratory draws will be delayed or deferred if the investigator believes that obtaining them might increase subject risk. Additionally, a study-related laboratory specimen that is unevaluable due to clotting or laboratory related issues will not be repeated. If a study related laboratory draw is delayed or deferred, study staff will document this on a source document.

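### The creatinine that Section 7.3.3 ties to the optional Period 4 PK is not scheduled as such in Appendix A, and its 0.25 mL is left out of the Period 4 blood volume

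*Protocol*

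**What the plan says.** Protocol Section 7.3.3 (Period 4, Study Assessment Days 18 to 24) sets two conditions for serum creatinine: "Obtain if the ganciclovir pharmacokinetics are being obtained during this study assessment period" and "To be drawn on the calendar day that ganciclovir PKs are being drawn". In the same list, hematology, AST and ALT are limited to clinically indicated draws; creatinine is not.

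Section 8.2 gives the general rule, "Chemistry labs (serum creatinine) will be drawn on the calendar day that ganciclovir PKs are being drawn", with the volume: "required amount of whole blood for serum creatinine is 0.25 mL". Section 4 gives the purpose. It says "serum creatinine will be drawn for the research protocol on the day that the ganciclovir pharmacokinetic specimens are obtained", so that creatinine clearance can be calculated and ganciclovir clearance related to renal function.

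The Appendix A schedule handles Period 4 differently. Its creatinine row carries footnote g (same day as PK) in Period 1 only, and footnote e in Periods 2 to 7. Footnote e reads "If being drawn for clinical reasons; any laboratory value obtained during the window will suffice", adds a preference for the most abnormal result, and requires no source documentation. The volume row gives Period 4 as 0.5 mL, or 1.5 mL with the second PK.

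SAP Table 1 prints the same Period 4 volumes and the same footnote wording. As far as its broken layout can be read, it too shows footnote g in Period 1 only.

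**The concern.** The text and the schedule give a site different instructions for the same visit.

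Under Section 7.3.3, a second PK always comes with a creatinine from that day. Under Appendix A it may come with a creatinine from another day in the window, with one chosen because it was abnormal, or with none. The omission could also go unrecorded: footnote g asks for a delayed or deferred draw to be documented, whereas footnote e does not.

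Two things are at stake:

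- **Analysis.** Relating ganciclovir clearance to renal function is a stated purpose of the PK-day creatinine, and renal function is an example covariate in the analysis plan. Clearance and creatinine from different days weaken that relation at the second PK.
- **Blood volume.** The schedule states the research volume per period for infants who may weigh as little as 500 g at enrollment, under a limit of 7 mL/kg over 42 days. A site that follows Section 7.3.3 with a research draw takes more than the schedule shows.

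**Working it through.** **Inputs**

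- PK sample, Section 7.3.3: "Required amount of whole blood for plasma ganciclovir determination at each timepoint is 200" microlitres, that is 0.2 mL at each of five time points, or 5 x 0.2 = 1.0 mL.
- Viral load, Section 7.3.3: "required amount of whole blood for CMV PCR is 0.5 mL".
- PK-day creatinine, Section 8.2: 0.25 mL.
- Limit and cut-off, Appendix A footnote j: 7 mL/kg over 42 days; no second PK below 575 g.
- Printed period totals in both schedules: 1.75, 0.5, 0.5, then 0.5 or 1.5 mL for Periods 1 to 4.

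**Step 1: reproduce the printed totals**

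- Period 1: 1.0 (PK) + 0.25 (creatinine) + 0.5 (PCR) = 1.75 mL. This matches, so creatinine is counted there.
- Period 4 with PK: 1.0 (PK) + 0.5 (PCR) = 1.5 mL. This matches only if creatinine counts as zero.

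**Step 2: apply Section 7.3.3 with a research draw**

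- Period 4 with PK: 1.0 + 0.5 + 0.25 = 1.75 mL.
- Difference from the printed figure: 0.25 mL. At 575 g that is 0.25 / 0.575 = 0.43 mL/kg.

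**Step 3: cumulative volume through Period 4, all draws taken**

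| | Cumulative volume | Per kg at 575 g | Weight at which it equals 7 mL/kg |
|---|---|---|---|
| As tabulated | 1.75 + 0.5 + 0.5 + 1.5 = 4.25 mL | 4.25 / 0.575 = 7.39 mL/kg | 4.25 / 7 = 607 g |
| With second creatinine | 1.75 + 0.5 + 0.5 + 1.75 = 4.50 mL | 4.50 / 0.575 = 7.83 mL/kg | 4.50 / 7 = 643 g |

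At 575 g the limit allows 7 x 0.575 = 4.025 mL. On this count the tabulated volume is already above the limit before the second creatinine is added.

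**Step 4: timing**

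Days 18 to 24 make a window of 24 - 18 + 1 = 7 days. Footnote e accepts a creatinine from any of them; Section 7.3.3 accepts only the PK day.

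**The case against.** **Only one section names Period 4.** Section 7.3.3 alone ties a creatinine to the second PK explicitly. Sections 4 and 8.2 state a general PK-day rule, and the Section 4 paragraph on the second PK mentions PK samples and no creatinine. Section 7.3.3 also says to obtain the test without calling it a research draw. This stands, and a reader should not infer that several sections independently name a Period 4 research creatinine. The conflict remains, because Section 7.3.3 is explicit and the general rule agrees with it.

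**The forms need not follow the schedule.** SAP Appendix C, item 4.2.2, has the eCRFs compared with the schedule, the protocol narrative and the MOP. That check could catch the mismatch, so the documents do not support the claim that forms will be built to the schedule alone. It cannot settle the matter, though, since two of its three sources disagree.

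**The SAP table is weak evidence.** Its creatinine row shows one footnote g and a single footnote e with blank cells. Appendix A is the firm source for the footnotes. The 1.5 mL is legible in both.

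**The effect is narrow.** The second PK is optional and at the treating physician's request. No listed endpoint relates clearance to renal function, and as a covariate renal function appears only as an example if a population approach is used. All of this stands.

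**A stronger reading is that renal function at the second PK is biased low by a stated percentage.** A reader might infer this from the preference for abnormal values. It would need an assumed excess of the most abnormal creatinine over the same-day value, and would need that value to enter the analysis. The documents give neither.

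**Conclusion.** The inconsistency is real and limited. Section 7.3.3 requires a PK-day creatinine with the second PK; the Appendix A footnote for that cell does not, and both schedules omit its blood. With a research creatinine the Period 4 volume is 1.75 mL, not 1.5 mL. If a clinical creatinine taken the same day serves, 1.5 mL is correct, so the printed figure is not wrong for every infant.

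Only subjects with a second PK are affected. The AUC12 from the first PK is untouched, because Period 1 carries footnote g and counts the creatinine. The size of any bias in estimated renal function cannot be derived from the documents.

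The 7.39 and 7.83 mL/kg figures assume that every Period 1-4 draw is taken and that 575 g is the denominator for the whole cumulative volume. They do not show that any infant would exceed the limit, since draws may be deferred or missed. They do show that the volumes, the limit and the cut-off do not fit together on the plan's own numbers.

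**What to change.** Reconcile Sections 7.3.3 and 8.2, Appendix A and SAP Table 1 on the Period 4 creatinine. If the Section 7.3.3 rule is kept:

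1. In both schedules, mark the Period 4 creatinine cell with footnote g when the second PK is done and footnote e otherwise.
2. Show the Period 4 volume as 0.5 mL without PK and up to 1.75 mL with PK (1.5 mL if a same-day clinical creatinine is used).
3. State in protocol Section 11.4 and the SAP data analysis plan that the same-day creatinine is the value paired with second-PK clearance.

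In the same revision, re-check the volumes against the 7 mL/kg limit and the 575 g cut-off in footnote j, and say which weight and which draws the limit counts. The volumes and the cut-off must be reconciled together; this review does not say which figure should change.

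The cost is a few table cells, a footnote and one sentence in each document. The blood-volume check is the larger part, because writing in 1.75 mL alone would widen the gap to the stated limit.
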